5.2 GENERAL CONCOMITANT MEDICATION AND SUPPORTIVE CARE GUIDELINES

5.2.1 Concomitant medications

A concomitant medication is any medication a patient entering the trial is using and is expected to continue using for some portion of the trial as well as any medication the patient uses during the course of the trial. Study drugs are not considered concomitant medication.

- 5.2.2 All concomitant medications recorded at trial entry must have a related, ongoing concomitant illness listed under the medical history at the time of patient entry into the trial unless the medication is used for prophylaxis. Patients may continue to use any ongoing medications not prohibited by the protocol.

- 5.2.3 All prescription and over-the-counter medications at trial entry as well as any new medications started during the trial must be documented. The documentation should continue until 30 days from the end of the last study drug treatment.

- 5.2.4 No other anti-cancer therapy including chemotherapy, radiation therapy, hormonal cancer therapy and immunotherapy, or experimental medications are permitted while the patient is on this trial.

- 5.2.5 Any disease progression that requires other specific anti-tumor therapy will be cause for discontinuation from study medication.

- 5.2.6 Steroid use is not recommended during sunitinib treatment unless absolutely necessary (e.g., for treatment of adverse events or protocol-required premedication) because many steroids (e.g., prednisone, prednisolone, dexamethasone, etc.) effectively lower sunitinib exposure through CYP3A4 interactions. Also steroids are known to have anti-tumor activity in thymic malignancies.

- 5.2.7 The case report form (CRF) must capture the concurrent use of all other drugs, over-the-counter medications, or alternative therapies.

- 5.2.8 The Principal Investigator should be alerted if the patient is taking any agent known to affect or with the potential to affect selected CYP450 isoenzymes. A comprehensive list of CYP3A4 inhibitors, inducers, and substrates is provided (see [Appendix C](#)).

- 5.2.9 In addition, patients and their caregivers should be provided the patient information sheet (see [Appendix H](#)) describing potential interactions of the study agents with other drugs, remedies, and medications.

5.2.10 Use of agents with proarrhythmic potential (terfenadine, quinidine, procainamide, disopyramide, sotalol, probucol, bepridil, haloperidol, risperidone, indapamide, and flecainide) is not permitted during treatment with sunitinib. A comprehensive list of agents with proarrhythmic potential can be found at <http://torsade.org>.

5.2.11 **Cytochrome P450-3A4 (CYP3A4) inhibitors and/or inducers:** Patients must not have received potent inhibitors within 7 days and potent inducers within 12 days prior to drug administration.

Sunitinib is primarily metabolized by liver enzymes, in particular CYP3A4. There was a mean 1.8-fold increase in exposure of SU011248 when co-administered with ketoconazole, a strong inhibitor of CYP3A4 and a mean 4-fold decreased in exposure of SU011248 when co-administered with rifampin, a strong inducer of CYP3A4.

Therefore, co-administration with strong inhibitors (grapefruit/grapefruit juice, ketoconazole, itraconazole, clarithromycin, indinavir, saquinavir, ritonavir, atazanavir, nelfinavir, nefazodone, voriconazole, telithromycin) and strong inducers (dexamethasone, rifampin, rifabutin, rifapentin, carbamazepine, phenobarbital, phenytoin, St. John's wort) of CYP3A4 may result in significant increases/decreases in exposure of SU011248 and may alter the safety/efficacy of the drug. However for patients who are on ritonavir, sunitinib may be administered at a starting dose of 37.5 mg q day.¹⁴²

Strong CYP3A4 inhibitors and inducers are not permitted 7 and 12 days before dosing, respectively. During the study, strong CYP3A4 inhibitors and inducers are not recommended. Alternative therapies should be used when available. If usage of a strong CYP3A4 inhibitor or inducer is necessary, this must be in agreement with the Sponsor. The following drugs should not be used before or during the study:

Inhibitors – prohibited 7 days before dosing and during study.

azole antifungals (ketoconazole, itraconazole)	diltiazem
clarithromycin	verapamil
erythromycin	

Inducers – prohibited 12 days before dosing and during study.

rifampin	phenobarbital
rifabutin	phenytoin
carbamazepine	St. John's wort

Aprepitant, fluconazole and voriconazole are clinically relevant moderate CYP3A4 inhibitors that should be avoided, if possible, or used with great caution.

Additional inducers or inhibitors of CYP3A4 can be found at <http://medicine.iupui.edu/clinpharm/ddis>. Interacting drugs with sunitinib should be avoided or used with great caution.

A comprehensive list of CYP3A4 inhibitors, inducers, and substrates is provided in [Appendix C](#). In addition, patients and their caregivers should be provided the patient information sheet (see [Appendix E](#)) describing potential interactions of sunitinib with other drugs, remedies, and medications.

5.2.12 The use of coumarin-derivative anticoagulants such as warfarin (Coumadin®) is not recommended, although doses of up to 2 mg daily are permitted for prophylaxis of thrombosis.

5.2.13 Supportive care guidelines

- **Nausea/vomiting** – Patients with treatment-related nausea should be treated initially with a phenothiazine (prochlorperazine – 10 mg every 8 hours orally as needed or promethazine – 12.5-25 mg IV every 6 hours as needed). If this is inadequate, a benzodiazepine should be added until acute nausea is controlled or toxicity is limiting. Should this prove inadequate acutely, a steroid may be added (*e.g.*, dexamethasone 4 mg every 6 hours as needed).

After acute nausea has resolved, consideration should be given to initiation of prophylactic anti-emetic therapy. If nausea recurs despite reasonable medical intervention (as outlined above), dose reduction will be needed as described in Section 6.

- **Diarrhea** should be managed with loperamide: 4 mg at first onset, then 2 mg every 2-4 hours until diarrhea is controlled (maximum = 16 mg loperamide per day).
- **Hand-foot syndrome** may be treated with topical emollients (such as Aquaphor), topical/systemic steroids, and/or antihistamine agents. Vitamin B6 (pyridoxine; 50-150 mg orally each day) may also be used. Avoid exposure to heat, hot water, pressure, or friction. Use of soft, well-fitting shoes may help, as may use of acetaminophen if needed for analgesia.
- Patients with **neutropenic fever** or infection should be evaluated promptly and treated with IV antibiotic therapy or therapeutic colony-stimulating factors as appropriate following the ASCO guidelines [*J Clin Oncol* 18(20):3558-85, 2000]. Packed red blood cell and platelet transfusion should be administered as clinically indicated. Erythropoietic agents may be used at the discretion of the treating physician.

5.3 DURATION OF THERAPY

In the absence of treatment delays due to adverse event(s), treatment may continue until one of the following criteria (off treatment criteria) applies:

- Disease progression,
- Intercurrent illness that prevents further administration of treatment,
- Unacceptable adverse event(s),
- Delay of treatment of ≥ 3 weeks,
- Positive pregnancy test
- Patient decides to withdraw from the study, or
- General or specific changes in the patient's condition render the patient unacceptable for further treatment in the judgment of the investigator.

5.4 DURATION OF FOLLOW UP

Prior to documenting removal from the study, effort must be made to have all subjects complete a safety visit approximately 30 days following the last dose of study therapy; then patients will be followed either with clinic visits or phone interviews yearly until death. Patients removed from treatment for unacceptable adverse event(s) will be followed clinically until resolution or stabilization of the adverse event, and then via clinic visits or phone interviews yearly until death.

The following information will be collected:

- Date of follow up
- Is patient dead or alive?
- If dead, document exact date of death.
- Further treatment(s), if any
- Document date of disease progression

5.5 CRITERIA FOR REMOVAL FROM STUDY

5.5.1 Once a patient has been removed from study, no further data can be collected; therefore, with completion of the duration of follow-up described in Section 5.4, the criteria for removal from study are:

- Lost to follow-up
- Death, or
- The patient decides to withdraw from the study.

The reason for study removal and the date the patient was removed must be documented in the database.

5.5.2 Off Protocol Therapy and Off Study Procedure

Authorized staff must notify the NCI Central Registration Office (CRO) when a patient is taken off protocol therapy and when a subject is taken off study. The CRO is open from 8:30am to 5:30pm EST Monday through Friday, excluding federal holidays. A Participant Status Update Form from the web site (<http://home.ccr.cancer.gov/intra/eligibility/welcome.htm>) main page must be completed and sent via encrypted email to: NCI Central Registration Office [contact]. The Participant Status Update Form will be supplied by the CCR study coordinator. Send the completed form to the CCR study coordinator.

6 DOSING DELAYS/DOSE MODIFICATIONS

6.1 GENERAL GUIDANCE

6.1.1 Patients may continue to receive therapy provided the following criteria are met on day 1 of each cycle:

- ANC \geq 1,000/mcL
- Platelets \geq 75,000/mcL
- Non-hematologic toxicity recovered to < grade 2 (or tolerable grade 2 or baseline)
- No evidence of progressive disease

6.1.2 In the event of an adverse event at least possibly related to the agent, the doses of such agent should be adjusted according to the guidelines shown in the Dose Delays / Dose Modifications tables shown below. If a patient experiences several adverse events and there are conflicting recommendations, the investigator should use the recommended dose adjustment that reduces the dose to the lowest level. If an adverse event is not covered in such tables, doses may be reduced or held at the discretion of the investigator for the subject's safety. Subjects with adverse events that are manageable with supportive therapy may not require dose reductions (e.g., nausea/vomiting may be treated with antiemetics, diarrhea may be treated with loperamide, and electrolyte abnormalities may be corrected with supplements rather than by dose reduction).

6.1.3 Subjects will be withdrawn from the study if they fail to recover to CTC Grade 0-1 or tolerable grade 2 (or within 1 grade of starting values for pre-existing laboratory abnormalities) from a treatment-related adverse event within 21 days OR they experience agent related adverse events requiring dose modification despite two previous dose reductions (i.e. would require a 3rd dose reduction) unless the investigator and CTEP monitor agree that the subject should remain in the study arm because of evidence that the patient is/may continue deriving benefit from continuing study treatment (i.e. patient has PR, CR, SD > 3 months). The appropriate reduced dose will be determined after discussion between the principal investigator and CTEP monitor.

6.2 TREATMENT DELAYS AND MODIFICATIONS FOR ADMINISTRATIVE NEEDS

Brief interruptions and delays may occasionally be required due to travel delays, airport closure,

independent weather, family responsibilities, security alerts, and government holidays, etc. Delays of up to 1 week will not be considered protocol deviations and will not be separately reported. If a patient takes 75% or more of scheduled doses during a cycle, missed doses will not be reported as deviations. If the study team instructs a patient to hold the investigational drug, it will not be considered a protocol deviation. A patient that interrupts therapy for more than 3 weeks will be taken off treatment.

6.3 TREATMENT DELAYS AND MODIFICATIONS FOR MEDICAL NEEDS

Patients experiencing complications of their disease or other medical illness not attributable to disease progression, or protocol therapy may also require brief interruptions and delays that will not be considered protocol deviations, and will not be separately reported. A patient that interrupts therapy for more than 21 days will be taken off treatment.

6.4 SUNITINIB MONOTHERAPY DOSE LEVEL REDUCTIONS (GROUPS 1 AND 2)

Dose Level	Sunitinib Dose
Starting Dose	50 mg once a day
First Dose Reduction	37.5 mg once a day
Second Dose Reduction	25 mg once a day

6.6 DOSAGE MODIFICATION CRITERIA FOR OTHER HEMATOLOGIC AND NON-HEMATOLOGIC ADVERSE EVENTS

Event	AE Grade or Observation	Dose modification
Neutropenia	Grades 1 and Grade 2 \geq 1200	Maintain dose

Event	AE Grade or Observation	Dose modification
	Grade 2 < 1200 and Grade 3*	Hold sunitinib until ANC \geq 1000, then reduce 1 dose level and resume treatment
	Grade 4	Hold sunitinib until ANC \geq 1000, then reduce 1 dose level and resume treatment
Thrombocytopenia	Grade 1	Maintain dose
	Grades 2 and 3*	Hold sunitinib until platelets \geq 75, 000, then reduce 1 dose level and resume treatment
	Grade 4	Hold sunitinib until platelets \geq 75, 000, then reduce 1 dose level and resume treatment
Fever or flu-like symptoms	Grades 1-4	Maintain dose
Fatigue (lethargy, malaise, asthenia)	Grades 1 and 2	Maintain dose
	Grade 3* and severe grade 2, at investigator discretion	Hold sunitinib until \leq grade 2, then reduce 1 dose level and resume treatment
QTc prolongation Do not use CTCAE v5 grades	>450 but < 550 msec	Review patient's concomitant medications for QT interval-prolonging agents. Correct any electrolyte abnormalities. Continue sunitinib at current dose level.
	\geq 550 msec	Stop sunitinib and any other QT-interval prolonging agents immediately. Correct any electrolyte abnormalities, then: If there is a plausible explanation for AE other than sunitinib treatment, resume sunitinib at current dose level. If sunitinib may have contributed to the AE: Reduce 2 dose levels and restart sunitinib. If QTc remains <500 msec after 14 days at reduced dose, increase one dose level and continue sunitinib. If QTc remains <500 msec after 14 days, original dose of sunitinib may be resumed.

Event	AE Grade or Observation	Dose modification
Hand-foot syndrome	Grades 1 and 2	Maintain dose
	Grade 3*	Hold sunitinib until \leq grade 1, then resume treatment at same dose or reduce 1 dose level
AST and/or ALT elevation (SGOT, SGPT)	Grades 1 and 2	Maintain dose
	Grades 3 and 4	Sunitinib should be dose delayed if elevation of ALT is $>5 \times$ ULN, AST is $>5 \times$ ULN, and/or bilirubin is $>3 \times$ ULN. Sunitinib may be re-administered when levels of ALT and AST are $\leq 5 \times$ ULN and bilirubin is $\leq 3 \times$ ULN. Sunitinib should NOT be re-administered if subjects develop \geq grade 3 hepatic failure (CTCAE v5 definition). Patients must have LFTs checked at baseline and during each treatment cycle. LFTs should be obtained at any time when they are clinically indicated.

6.7 MANAGEMENT OF OTHER CLINICALLY SIGNIFICANT SUNITINIB-RELATED AEs

(not specifically addressed above)

Observation	Action
AE resolves promptly with supportive care	Maintain dose level
1. Grade 3 or higher (non-hematologic or grade 4 (hematologic) AE related to sunitinib and lasting >5 days that does not resolve to grade 2 or below despite maximum supportive care for < 48 hours.	Reduce one dose level
AE does not resolve to grade 2 or below after treating patient at the lowest (i.e., 25* mg or 12.5* daily) reduced dose level.	In general, remove patient from study**
* 25 mg if the patients start dosing at 50 mg on a 4/2 schedule (solid tumors) or 12.5 mg if patients start dosing at 37.5 mg ** After consultation with study sponsor (DCTD, NCI), a dose of 25 mg daily may be considered for patients on study ≥ 3 months who are benefiting from the agent.	

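### The first row of the 6.7 dose table has no grade limit, so a promptly treated life-threatening reaction such as anaphylaxis is left with a same-dose default

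*Combined protocol and SAP*

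**What the plan says.** Section 6.7 covers clinically significant sunitinib-related events that are "not specifically addressed above", that is, without a rule in 6.5 (with Appendix G) or 6.6. It has three rows.

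- Row 1: the "AE resolves promptly with supportive care". The dose is kept. No grade, seriousness or event type is stated.
- Row 2: an "AE related to sunitinib and lasting >5 days that does not resolve to grade 2 or below". The row starts at grade 3 for non-hematologic events and at grade 4 for hematologic ones. The dose goes down one level.
- Row 3: an event that stays above grade 2 at the lowest dose level. In general, the patient is removed.

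Section 6.1.2 gives the tables their force. Where sunitinib is a possible cause, its instruction is that "the doses of such agent should be adjusted according to the guidelines shown in the Dose Delays / Dose Modifications tables shown below". It adds: "If an adverse event is not covered in such tables, doses may be reduced or held at the discretion of the investigator".

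Section 5.3 lists the reasons for stopping treatment. Two are relevant here: unacceptable adverse events, which are not defined, and changes in condition that "render the patient unacceptable for further treatment in the judgment of the investigator".

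**The concern.** A dose-modification table is most needed when the event is dangerous and the site must act quickly. Here the row that fits a rapidly reversed life-threatening reaction tells the site to continue unchanged, with no hold and no consultation. Speed of recovery decides the action and severity plays no part. For an immediate hypersensitivity reaction, quick recovery under treatment says little about the safety of the next dose.

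The event is foreseeable. The adverse event list in 7.4.1.1 places allergic reaction among the rare but serious risks of sunitinib, and a footnote says that anaphylaxis and angioedema have been observed. At stake is the safety of a patient re-exposed to the suspected drug at full dose. The response-rate analysis is not affected.

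**Working it through.** The main check is one of logic. The test case is a grade 4 anaphylaxis attributed to sunitinib, treated, and resolved the same day.

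| Provision | What it needs | Test case |
|---|---|---|
| 6.5 and Appendix G | Hypertension | Does not apply |
| 6.6 | Neutropenia, thrombocytopenia, fever or flu-like symptoms, fatigue, QTc, hand-foot syndrome, AST/ALT | Does not apply |
| 6.7 row 1 | Prompt resolution with supportive care | **Met: keep the dose** |
| 6.7 row 2 | More than 5 days without falling to grade 2 or below | Not met |
| 6.7 row 3 | Persistence at the lowest dose level | Not met |
| 6.1.1 | On day 1 of a cycle, non-hematologic toxicity recovered to below grade 2 (or tolerable grade 2 or baseline) | Passes, so treatment may continue |
| 6.1.2 discretion to reduce or hold | Event not covered by the tables | On its wording not reached, because row 1 covers the event |
| 6.1.3 | Failure to recover within 21 days, or need for a third dose reduction | Not met |
| 3.2.8 | Allergy to similar compounds, as history at entry | Does not govern a reaction on study |
| 5.3 | Unacceptable event, or investigator judgment | Available, but undefined and discretionary |

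Among the provisions that prescribe a dose action, only row 1 matches.

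Two rules show that the protocol does write firmer actions for severe events. Appendix G stops sunitinib for grade 4 hypertension, then requires either permanent discontinuation or a restart one level lower after consultation with the Principal Investigator. The AST/ALT rule in 6.6 bars re-administration after hepatic failure of grade 3 or worse. Nothing equivalent exists for anaphylaxis or for other grade 4 events that fall to 6.7.

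**Size.** The only frequency given for allergic reaction is the band below 3%, without a split by grade or speed of recovery. If that band is assumed to apply here, the expected number of allergic reactions of any kind is below 0.03 × 15 = 0.45 in Group 2 and below 0.03 × 58 = 1.74 at the full accrual ceiling in 17.2. This is a ceiling for one event type, not an estimate of how many patients would meet the row 1 default.

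**The case against.** The strongest reply is that 5.3 decides whether a patient stays on drug, and 6.7 only chooses a dose for those who do. The first half stands: a site may stop treatment after anaphylaxis at once. Under 6.2, a hold ordered by the study team is not even a deviation. The second half is weaker, because row 3 of 6.7 itself directs removal, so the table does speak to stopping where its authors wanted it to.

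A second reply reads row 1 as shorthand for the sentence in 6.1.2 that events manageable with supportive therapy may not need a dose reduction. That sentence is permissive, its examples are nausea, vomiting, diarrhea and electrolyte changes, and 6.1.2 calls the tables guidelines. This is probably what was intended. Row 1, however, carries over neither the permissive wording nor the mild examples.

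A third reply points to oversight. Under 7.4.2.3, a serious grade 4 event must be notified through CTEP-AERS within 24 hours, with a full report within 5 calendar days. Allergic reaction has no entry among the exceptions to expedited reporting. Section 7.4.2.1 sends the report automatically to the Principal Investigator, and 7.6.1 has the team discuss each patient at least weekly. These make an unreviewed re-dosing unlikely. They do not say what dose to give.

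A reader might also infer that transient ischemic attack falls into the same trap. The documents do not clearly support that. Such an event clears by itself rather than through supportive care, so it fits row 1 only arguably; if it does not fit, the 6.1.2 discretion applies.

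Nor is it sound to argue that row 1 is out of line because most event-specific rules require a hold at their worst category. Most of the 6.6 holds last only until recovery, and a row 1 event has already recovered. Fever and flu-like symptoms keep the dose at all grades, and of these rules only Appendix G requires consultation.

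**Conclusion.** The point holds in a limited form. For a grade 4 sunitinib-related event that resolves promptly and has no rule in 6.6 or Appendix G, the only matching table action is to keep the same dose. A reader might go further and say that the protocol requires rechallenge after anaphylaxis. It does not, because 5.3 permits stopping at every site.

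What remains is a safety default that points the wrong way, with protection resting on an undefined stopping criterion, clinical judgment and prompt reporting. That is minor. The conclusion assumes that row 1 is read on its words and that the event is attributed to sunitinib. No count of affected patients can be given.

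**What to change.** Amend 6.7 as follows.

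- Limit row 1 to events below grade 4. Except isolated, correctable laboratory abnormalities, in keeping with 6.1.2, where "electrolyte abnormalities may be corrected with supplements rather than by dose reduction".
- Exclude anaphylaxis and angioedema from row 1 at any grade. After either, discontinue sunitinib permanently as an unacceptable adverse event under 5.3.
- For other grade 4 non-laboratory related events, hold sunitinib, then either discontinue or restart one dose level lower after consultation with the Principal Investigator, as Appendix G does for grade 4 hypertension.
- A patient already at the lowest level discontinues. Under the 6.7 footnote that level is 25 mg after a 50 mg start, or 12.5 mg after a 37.5 mg start.

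This does not make the table exhaustive. A grade 3 non-hematologic event that lasts 3 to 5 days without prompt resolution still matches no row and stays with the investigator's discretion under 6.1.2.

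The cost is one short text amendment with a cross-reference to 5.3, and no added visits, tests or patients. The downside is that an occasional patient who is benefiting stops or restarts at a lower dose.

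### The only dose-reduction row in Section 6.7 caps supportive care at under 48 hours where a minimum is needed, so it does not order a reduction for a promptly treated, refractory patient

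*Combined protocol and SAP*

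**What the plan says.** Section 6.7 is a three-row table for sunitinib-related events not dealt with earlier in Section 6.

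- Row 1, "AE resolves promptly with supportive care": keep the dose.
- Row 2 orders a one-level dose reduction. It is for sunitinib-related events of at least Grade 3 when non-hematologic, or of grade 4 when hematologic. Its time condition reads: "lasting >5 days that does not resolve to grade 2 or below despite maximum supportive care for < 48 hours".
- Row 3, "AE does not resolve to grade 2 or below after treating patient at the lowest" reduced dose level: in general, remove the patient from study.

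Section 6.4 sets three levels: 50 mg, then "37.5 mg once a day", then 25 mg. Section 6.1.2 makes the tables the first instruction. For an event that they do not cover, "doses may be reduced or held at the discretion of the investigator". For comparison, the Grade 3 fatigue row in Section 6.6 says to hold sunitinib until recovery to grade 2 or below, "then reduce 1 dose level and resume treatment", with no limit on event duration or on time spent on supportive care.

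**The concern.** Row 2 describes treatment failure: the event has persisted and supportive care has not brought it down. Such a rule needs a minimum time on care, so that care has had a fair trial. The row gives a maximum instead, and pairs it with an event that must already have lasted more than five days. Those conditions sit together only when maximum care started late. Taken literally, the row orders a reduction for the patient whose care was delayed and not for the patient who was treated at once and did not respond.

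What is at stake is one compulsory safety trigger. Safety and tolerability is a secondary objective, and Group 2 was opened partly to see whether the modified schedule is better tolerated.

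**Working it through.** **Inputs**

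- Event duration limit: more than 5 days = 5 × 24 = 120 h (Section 6.7, row 2).
- Limit on maximum supportive care: under 48 h (same row).
- Dose levels: 50, 37.5 and 25 mg (Section 6.4).
- *s*, the hours from onset to the start of maximum care. The protocol gives no value, so it is varied from 0 to 120 h.

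**Timing.** At event hour *D*, time on maximum care is *D* − *s*. If both limits are judged together, the row needs *D* > 120 and *D* − *s* < 48. Hence *s* > *D* − 48 > 120 − 48 = 72 h.

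| Care starts (h after onset) | Care received when event reaches 120 h | Under 48 h? | With a 48 h minimum, row is met |
|---|---|---|---|
| 0 | 120 h | No | once past 120 h |
| 24 | 96 h | No | once past 120 h |
| 48 | 72 h | No | once past 120 h |
| 72 | 48 h | No | once past 120 h |
| 96 | 24 h | Yes | from 96 + 48 = 144 h |
| 120 | 0 h | Yes | from 120 + 48 = 168 h |

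**Coverage by dose level**, for a patient who started at 50 mg, was treated promptly and remains at Grade 3:

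| Level | Row 1 | Row 2 | Row 3 |
|---|---|---|---|
| 50 mg | no, not resolved | no, care is past 48 h | no, not the lowest level |
| 37.5 mg | no | no | no |
| 25 mg | no | no | yes, in general remove |

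Two of the three levels have no applicable row.

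**Other provisions**

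- 6.1.1 sets recovery criteria for day 1 of a cycle. It delays the next cycle and does not change the dose.
- 6.1.2 permits a reduction or a hold and does not require either.
- 6.1.3 withdraws a patient who has not recovered "from a treatment-related adverse event within 21 days", with an exception for patients who are benefiting.
- 5.3 ends treatment for unacceptable events.

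None of these orders the step from 50 to 37.5 mg.

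**Reach.** The adverse event list in Section 7.4.1.1 has 17 terms in its likely (>20%) column. Fatigue and hand-foot syndrome have rows in Section 6.6: 17 − 2 = 15. Seven of the 15 are mucositis sites; counted once, 15 − 7 + 1 = 9. Section 5.2.13 says that nausea recurring despite treatment needs a dose reduction, so nausea comes out: 9 − 1 = 8. These are mucositis, vomiting, diarrhea, constipation, abdominal pain, dyspepsia, anorexia and dysgeusia. The sentence in Section 5.2.13 names nausea only, so vomiting stays in. The frequency band is not specific to Grade 3, so eight is an upper bound on the common event types concerned and does not measure how often the row would be needed.

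**The case against.** **The symbol may be a text-reading error.** The cell also has a stray list number and an unbalanced bracket. This cannot be excluded outright, but it is weak: the greater-than sign in the same cell and the at-least sign in the table's footnote both read sensibly.

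**The row does not say that both limits must hold at the same moment.** A patient refractory to 120 h of care was also unresolved at 47 h, and no expiry is stated for an order once triggered. This stands in part. A reader might infer that the row can never apply to early care, or that a reduction order lapses when care reaches 48 h. The text says neither; both depend on judging the two limits at one instant. But on the lenient reading the 48-hour limit excludes nobody who has received maximum care, so the reader must set aside the stated limit to reach a sensible rule.

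**The intended threshold is nowhere stated.** True. With a 48-hour minimum the clause also adds nothing to the five-day condition for care begun within 72 h. It would still do useful work for later starts, by requiring an adequate trial of care before reduction. Rows 1 and 3 and Section 6.1.2, which says that events manageable with supportive therapy may not need a reduction, all point to failure of supportive care as the trigger.

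**Other rules protect the patient.** They do soften the effect. Section 6.6 also deals separately with cytopenias, fatigue, QTc prolongation, hand-foot syndrome and transaminase elevation, and Appendix G with hypertension. The remaining events still lack a compulsory reduction.

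**Conclusion.** The row is wrong as written, and the matter is minor. On its plain reading it fits only care begun more than 72 h after onset and supplies no reduction order for a promptly treated, refractory event at 50 or 37.5 mg. This rests on judging the two time limits together and on the symbol having been read correctly from the source.

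A reader might go on to infer that patients were kept at full dose through Grade 3 toxicity, or that response results are affected. The documents support neither. Section 2.3.2 reports that 25 of 41 patients needed dose reductions. That does not show which rule was used, but it gives no sign that reductions were blocked. The intent is clear enough that investigators may well have applied it, so harm arises only where the row is followed literally.

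**What to change.** In the second row of Section 6.7, replace the less-than sign before 48 hours with an at-least sign (≥), after the sponsor confirms that this is the intended threshold. Leave Section 5.2.13 unchanged. The cost is one symbol in one table cell, with no added visits, data or analysis.
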